3.4.2 Rationale for Recommended Phase 2 Dose

As of Amendment 4, following review of available safety (refer to Section 3.2.4.1) and PK data, the decision has been made to choose the following as the recommended Phase 2 dose (RP2D) on a Q2W schedule of Sym015 (referenced as the Q2W RP2D):

- Loading dose of 18 mg/kg infused over 1.5 hours on Cycle 1/Day 1 (C1/D1)
- Followed by Q2W maintenance doses of 12 mg/kg infused over 1 hour beginning on Cycle 1/Day 15 (C1/D15)

The rational for this choice is based upon preliminary PK data from the initial 6 mg/kg Q2W (N=3, 2-3 cycles) and 12 mg/kg Q2W (N=3, up to Cycle 2/Day 1) cohorts treated in the dose-escalation phase of this trial. These data were used to establish a population PK model.

The summary PK parameters for these data, based on non-compartmental analysis, are listed in [Table 1](#).

Table 1 Preliminary Sym015 Geometric Mean PK Parameters

Dose Q2W	N	AUC _{0-336h} 1 st dose (h x µg/mL)	C _{max} 1 st dose (µg/mL)	C _{trough} 2 nd dose (µg/mL)	C _{max} 3 rd dose (µg/mL)	t _½ 1 st dose (h)
6 mg/kg	3	19400	146	35.9	196	158
12 mg/kg	3	40000	294	119	396	213 (n=1)

Abbreviations: AUC, area under the concentration-time curve in a dosing interval; C_{max}, maximum concentration; C_{trough}, trough concentration; h, hour; N, number of patients; Q2W, dosing every second week; t_½, elimination half-life

The model was used to simulate average and 90% confidence intervals for Sym015 PK profiles for the 18+12 mg/kg Q2W regimen, and demonstrated that pre-dose serum concentrations, C_{trough}, are likely to be above 100 µg/mL for the vast majority of patients for all dose administrations. The serum concentration of 100 µg/mL has been defined as an approximate threshold for clinical efficacy. This has been deduced from the 750 mg Q2W dose regimen of another anti-MET monoclonal antibody, emibetuzumab, which has shown signs of efficacy in patients with *MET*-amplified tumors ([23,28](#)). It is assumed that similar serum concentrations of Sym015 and emibetuzumab will result in similar clinical efficacy because similar potencies between the two compounds have been observed in preclinical *in vitro* and *in vivo* studies (refer to Investigator's Brochure). *In vivo* studies also support that efficacy can be expected at concentrations above 100 µg/mL for both compounds.

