8.4 Pharmacokinetic Assessments

PK samples will be taken according to the schedules shown in [Table 9](#).

Analysis of PK will be performed at a central laboratory. A detailed laboratory manual specifying sample collection, handling, storage, and shipment will be provided to the trial sites.

In the event that a collected serum sample is inadequate or insufficient for PK analysis, the analysis of PK can be done using an anti-drug antibody (ADA) serum sample from the same time point, if available.

Note: Comprehensive collection of clinical samples is critical to the conduct of this study. In situations where collection of EOI + 8h samples is logically difficult due to clinic staff availability, the observation period may be shortened and an "end of day" sample may be obtained at the latest practical time. Such an option (if to be routinely employed) is available only after previous discussion with and approval by the Sponsor.

Table 9 Schedule of Pharmacokinetic Assessments

		Cycle 1			Cycles Thereafter		EOT	IM FUP
Sampling Time	Window	D1-D3	D8	D15	D1	D15		
Part 1 / Part 2 Basket Cohort								
Prior to SOI	- 4 h	X		X ¹	X ¹	X ¹		
EOI	+ 10 min	X		X ¹	X ¹	X ¹		
EOI + 1 h	±15 min	X						
EOI + 2 h	±30 min	X						
EOI + 4 h	±30 min	X						
EOI + 8 h	±90 min	X						
EOI + 24 h	±6 h	X						
EOI + 48 h	±12 h	X						
During Visit	NA		X				X	X
Part 2 NSCLC Cohorts (effective with protocol v8.0; December 2018)								
Prior to SOI	- 4 h	X		X ¹	X ¹	X ¹		
EOI	+ 10 min	X		X ¹	X ¹	X ¹		
EOI + 4 h	±30 min	X						
EOI + 48 h	±12 h	X						
During Visit	NA		X				X	X

Abbreviations (in alphabetical order): D, day; EOI, End of Infusion, EOT, End of Treatment Visit; NA, Not Applicable; h, hour; min, minutes; 1M FUP, 1-Month Follow-up Visit; SOI, Start of Infusion

1) If Sym015 is paused, only one PK sample should be taken during the visit

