10. STATISTICS

10.1 Statistical Considerations and Analysis Plan

No formal hypothesis testing is planned. Descriptive statistics will be used to summarize the safety, tolerability, pharmacokinetics, and clinical activity of Sym015 in all patient cohorts.

Data will be described and summarized as warranted by sample sizes. Listings will be used in place of tables in the event of small sample sizes. Dose-escalation assessment will be based on the DLT-evaluable population, defined as patients who complete the DLT assessment window. All other analyses will be based on the safety-evaluable population, defined as all patients who receive any amount of the study drug.

Continuous variables will be summarized with the use of means, standard deviations, medians, and ranges; categorical variables will be summarized using counts and percentages. All summaries will be presented separately by cohort, in both Part 1 and Part 2 of the study.

All details of the data analyses will be described in the Statistical Analysis Plan.

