10.5.4 Pharmacokinetic Endpoints and Analyses

The PK endpoints will be derived based on the concentration time curves of Sym015, and the first infusion of Sym015 in both parts of the trial. Refer to [Table 11](#).

Table 11 PK Endpoints Definitions and Derivations

Symbol	Definition and derivation
C_{trough}	Trough concentration (i.e., concentration of Sym015 measured pre-infusion)
AUC_{τ}	Area under the concentration-time curve in a dosing interval (i.e., from time zero (end of infusion) up to 336 hours or 504 hours depending on regimes). AUC_{τ} will be calculated using the linear trapezoidal method and interpolated in case of measurements after 336/504 hours, or extrapolated using terminal rate constant and the last quantifiable concentration, C_z
C_z	Last quantifiable concentration. C_z is not an endpoint, but is used for derivation of endpoints
$AUC_{\text{norm, } \tau}$	Dose normalized area under the concentration-time curve in a dosing interval, calculated as AUC_{τ} divided by the dose infused
C_{max}	Maximum concentration
T_{max}	Time to reach maximum concentration
λ_z	Terminal rate constant (negative of the slope of an ln-linear regression of the un-weighted data considering the terminal phase of the concentration-time curve \geq limit of quantification. λ_z is not an endpoint, but is used for derivation of endpoints
$T_{1/2}$	Terminal elimination half-life, calculated as $\ln(2)/\lambda_z$
CL	Clearance (Dose/ AUC_{τ})
V_z	Volume of distribution during the terminal phase (CL/λ_z)

C_{max} , C_{trough} and T_{max} will be derived from observed data while AUC_{τ} , $AUC_{\text{norm, } \tau}$, CL, V_z , and $T_{1/2}$ will be estimated using non-compartmental methods and actual time points.

Individual curves of serum concentration versus time after the first dosing of Sym015 will be presented on log- and linear scale for all patients in the FAS. Furthermore, trough serum concentrations for the period from first dose to end of treatment will be presented on linear scale individual plots. In addition, mean concentration time curves will be presented on linear scale using nominal time point by cohort and trial part. All PK endpoints will be listed and summarized by cohort and trial part.

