21.7 Protocol Amendment 7 dated 07-Dec-2018

1. Effective with this protocol amendment, accrual to the Basket Cohort is suspended. Emerging literature allowed for the identification of specific tumor types that are more likely to respond to Sym015 treatment (e.g., NSCLC). With this change, a new cohort of NSCLC *MET*-amplified patients has been added to Part 2 of the trial design, for a total of three cohorts.
2. With the suspension of the Basket Cohort, NSCLC *MET*-amplified patients entered to the Basket Cohort will be counted toward the NSCLC *MET*-Amplified Cohort; NSCLC *MET*^{Ex14Del} patients entered to the Basket Cohort will be counted toward the NSCLC *MET*^{Ex14Del} Cohort; patients with both will be counted as *MET*-Amplified.
3. Updated clinical experience information have been added to the scientific background.
4. According to the ASCO/CAP guidelines for testing of HER2 amplification, *MET*-amplification may be defined as positive with a MET/CEP7 ratio of >2.2 (occasionally 2.0). Symphogen has opted to change the cutoff to ≥ 3.0 based on emerging data that suggest higher degrees of *MET*-amplification are associated with higher degree of response.
5. Specified that concomitant therapy with bisphosphonates and denosumab are allowed during the dosing portion of the trial.
6. Clarified that after the Screening assessments, targeted physical examination may be performed as indicated.
7. The number of pharmacokinetic timepoints have been reduced for patients entered to the NSCLC cohorts.
8. The mandatory post-dosing tumor biopsy scheduled to be performed at the EOC2 or upon disease progression is now optional.
9. Clarified that all analyses will be related to and used only in connection with the data collected in the present trial as well as future development of Sym015.
10. Clarified that EOC assessments may be performed at any time during the week prior to Day 1 of the next cycle, including Day 1 of the next cycle, prior to dosing.
11. Clarified that initial SAE and follow-up SAE information are to be submitted within 24 hours of awareness.
12. Due to the new cohort sample sizes, an initially planned interim analysis becomes obsolete and will no longer be performed.
13. Guidelines pertaining to the General Data Protection Regulation have been added.
14. Formatting adjustments, typographical corrections, outline modifications, and wording/abbreviation changes are included.

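### Table 11 fixes the linear trapezoidal rule for AUC over sampling gaps of 5 and 7 days, which overstates first-dose AUC on average by about 1.4% to 5%

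*Protocol*

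**What the plan says.** Protocol Section 10.5.4, Table 11, defines AUC over a dosing interval as running "from time zero (end of infusion) up to 336 hours or 504 hours depending on regimes" and says that it "will be calculated using the linear trapezoidal method and interpolated in case of measurements after 336/504 hours". The terminal rate constant is used only to extrapolate from the last quantifiable concentration, so the linear rule applies throughout the sampled interval. AUC, dose-normalised AUC, CL, Vz and half-life "will be estimated using non-compartmental methods and actual time points". CL is dose divided by this AUC, and Vz is CL divided by the terminal rate constant. "All PK endpoints will be listed and summarized by cohort and trial part".

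Table 9 (Section 8.4) gives two schedules. For Part 1 and the Basket Cohort, first-dose samples fall at end of infusion (EOI), then 1, 2, 4, 8, 24 and 48 h later, on Day 8, and before the Day 15 dose. The block headed "Part 2 NSCLC Cohorts (effective with protocol v8.0; December 2018") keeps EOI, 4 h, 48 h, Day 8 and pre-dose Day 15. Section 21.7 records the change: "The number of pharmacokinetic timepoints have been reduced for patients entered to the NSCLC cohorts".

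Table 1 (Section 3.4.2, "Preliminary Sym015 Geometric Mean PK Parameters") gives first-dose half-lives of 158 h at 6 mg/kg and 213 h at 12 mg/kg (n=1).

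**The concern.** Between two points on a convex declining curve, the chord lies above the curve. The linear rule therefore adds area in every declining gap, and adds more when the gap is long relative to the half-life. Here the last gap (168 h) is 0.8 to 1.1 half-lives long. The error has one expected direction, so averaging over patients does not remove it. It reaches three further endpoints through the definitions in Table 11. Its size depends on half-life and on sampling times, both of which can differ between the cohorts whose summaries will be read side by side. The protocol fixes the rule itself, so this is not a detail left open for the SAP.

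**Working it through.** **Inputs.** From Table 1: Cmax 146 and 294 µg/mL, half-life 158 and 213 h, AUC over 0–336 h of 19,400 and 40,000 h·µg/mL (6 and 12 mg/kg, N=3 each). From Table 9: nominal times 0, 1, 2, 4, 8, 24, 48, 168, 336 h (full) and 0, 4, 48, 168, 336 h (NSCLC). Assumed, because the documents give no figure: early-phase half-life 6 to 48 h; residual CV 5% to 20%.

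**The plan's own figure.** Table 1 AUC cannot be reproduced without individual concentrations. A one-exponential curve through Table 1 Cmax and half-life has area Cmax/k × (1 − e^(−336k)), with k = ln 2 / half-life:

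- 6 mg/kg: k = 0.004387 per h, area 25,659, against 19,400 stated.
- 12 mg/kg: k = 0.003254 per h, area 60,073, against 40,000 stated.

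The stated values are lower, which fits a faster early phase and does not show an error in Table 1.

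**Step 1: one gap.** For a gap of d hours, the ratio of linear to exact area is (kd/2) × (1 + e^(−kd)) / (1 − e^(−kd)).

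| Gap | Excess, 158 h | Excess, 213 h |
|---|---|---|
| 44 h (4 to 48 h, NSCLC only) | 0.3% | 0.2% |
| 120 h (48 h to Day 8, both) | 2.3% | 1.3% |
| 168 h (Day 8 to Day 15, both) | 4.5% | 2.5% |

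**Step 2: whole interval, one-exponential.** NSCLC schedule at 158 h: concentrations at 0, 4, 48, 168 and 336 h are 146.0, 143.5, 118.3, 69.9 and 33.4. The four trapezoids are 579 + 5,758 + 11,289 + 8,677 = 26,303, and 26,303 / 25,659 = 1.0251. The other cases follow in the same way.

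| Half-life | Full schedule | NSCLC schedule | Log-down, either |
|---|---|---|---|
| 158 h | +2.45% | +2.51% | 0% |
| 213 h | +1.44% | +1.47% | 0% |

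Moving Day 8 by its permitted 2 days gives +1.4% to +3.8%.

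**Step 3: with an early phase.** Take C(t) = A·e^(−at) + B·e^(−kt), with A + B equal to Table 1 Cmax, k from the Table 1 half-life, and B chosen so that the area equals Table 1 AUC. Over early half-lives of 6 to 48 h and both doses:

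| Rule | Full | NSCLC | NSCLC relative to full |
|---|---|---|---|
| Linear | +1.8% to +4.8% | +3.7% to +5.1% | +0.3% to +1.9% |
| Linear-up/log-down | +0.2% to +1.8% | +1.2% to +2.1% | +0.1% to +1.6% |

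If the Table 1 AUC was itself obtained with the linear rule, the upper ends for that rule become 5.3% (full), 5.7% (NSCLC) and 2.0% (NSCLC relative to full).

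**Step 4: individual patients.** With residual CV of 5% to 20%, simulated linear AUC exceeded true AUC in about 59% to 96% of patients. It was never below the log-down AUC computed from the same samples.

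**The case against.** The linear rule is a recognised non-compartmental method, and the protocol does not contradict itself here. Section 10.1 says "No formal hypothesis testing is planned", PK endpoints are only listed and summarised, and the recommended Phase 2 dose rests on a population PK model and simulated trough concentrations. All of that stands and limits the point to a small accuracy gain.

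Three stronger readings are tempting, and the documents do not support them:

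- *AUC is too high in every patient.* With assay error this is a mean bias. It holds for each patient only relative to the log-down rule on the same data.
- *The 5- and 7-day gaps make the NSCLC cohorts worse.* Both schedules share those gaps. The extra NSCLC error comes from the 4 to 48 h gap alone: 0.03 to 0.06 percentage points for a one-exponential decline, and up to about 2% only with an assumed early phase.
- *A comparison or dose choice is compromised.* No test or decision rule uses this AUC.

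The direction itself can be questioned. Section 3.2.3 reports monkey half-lives of 8–23 days initially and 5–8 days terminally, so decline speeds up. Piecewise curves with those half-lives (switch at an assumed 72 to 264 h) gave −2.8% to +3.2% for the linear rule and −3.8% to 0% for log-down. The human figures point the other way: a decline that speeds up would put AUC above the one-exponential value, whereas Table 1 AUC lies well below it.

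Finally, dose divided by first-interval AUC is not total clearance. On a one-exponential curve, 23% to 34% of the total area lies beyond 336 h, so first-dose CL is overstated by about 30% to 50%. Correcting AUC alone moves CL slightly further in that direction. That is true, but it is a separate matter of how CL is defined and no reason to keep a biased AUC.

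**Conclusion.** The point holds as a minor one. The prescribed rule overstates mean first-dose AUC by 1.4% to 2.5% on the protocol's own half-lives if decline is one-exponential, and by up to about 5% if there is an early phase as Table 1 suggests. Dose-normalised AUC carries the same error; CL and Vz carry it with opposite sign. The NSCLC schedule adds 0% to 2%.

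The sizes rest on nominal sampling times, on Table 1 values from three patients per dose (one for the 213 h half-life), and on an assumed early half-life of 6 to 48 h. The upward direction rests on a convex decline, which the human data favour but do not prove.

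**What to change.** In Table 11, replace *linear trapezoidal method* with *linear-up/log-down trapezoidal method*, for all cohorts and both parts, and re-derive Part 1 AUC with the same rule so that results stay comparable.

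Add a note to the by-cohort PK summaries that NSCLC and earlier cohorts were sampled on different schedules. It is needed because log-down removes only part of that difference; about 0.1% to 1.6% remains in the curves with an early phase. Identifying the schedule per patient would be safest, since Section 5.5 counts NSCLC patients who entered through the Basket Cohort toward the NSCLC cohorts, while the reduced schedule took effect only with version 8.0.

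The cost is a software setting, a re-run and one footnote. No patient, visit or sample is affected.

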10.5.5 Additional Endpoints and Analyses

The following additional endpoints will be assessed in Part 1 and Part 2 of the trial:

- Part 1 only: MET-receptor down-regulation measured by percentage and nominal change in target expression from baseline to EOC2 or PD (whichever comes first) in skin biopsy samples
- Biomarkers relevant to Sym015 activity
- Tumor genetics, drug target genes, and other biomarker genes that are known to be involved in the development and progression of *MET*-amplified solid tumor malignancies

The additional endpoints, outlined above may include genes that are unknown or have not been included in the scientific hypotheses of this trial, but that, during the collection of data from this trial, may evolve as new candidate genes and markers related to Sym015 safety, efficacy, or mechanism of action.

Percentage and nominal change in target expression from baseline to EOC2 or PD (whichever comes first) in skin biopsy samples will be presented. Descriptive statistics will be used, including scatter plots of values at EOC2 versus baseline.

Potential biomarkers include genes, gene transcripts, and proteins of RTKs and molecules of the MET signaling pathway. All biomarkers will be listed and descriptively summarized.

Exploratory analyses using the biomarkers might be performed.

10.6 Interim Analysis

No interim analysis is planned.

10.7 Deviations from the Statistical Plan

Any deviation(s) from the original analysis plan will be described in a protocol amendment and/or in a statistical analysis plan and/or in the final CTR, as appropriate.

11. ETHICS

11.1 Institutional Review Board/Ethics Committee

An IRB/EC will review the protocol and any amendments and advertisements used for recruitment, as well as the informed consent documents, their updates (if any), and any other written materials given to the patients. The CTR will include a list of all IRBs/ECs to which the protocol has been submitted and the name of the committee chair.

11.2 Patient Information and Informed Consent

The Investigator or his/her designee must obtain written informed consent from each patient before any trial related procedures are performed. Each patient must receive full patient information before giving consent. The patient information must contain full and adequate verbal and written information regarding the objective and procedures of the trial and the possible risks involved.

Before signing the informed consent form the patient must be given sufficient time to consider his/her possible participation. Each patient must also be informed about his/her right to withdraw from the trial at any time.

Each patient must sign the informed consent form; the patient receives a copy of the signed form and the original is retained in the Investigator Site File (ISF). The informed consent form must be signed and dated both by the patient and by the Investigator or designee providing the information to the patient.

12. SAFETY SURVEILLANCE SET-UP

12.1 Safety Review

An SMC will be established. This committee will include Investigator(s), Medical Monitor(s), Drug Safety Physician, and Sponsor's medical representatives. The SMC will review clinical and laboratory safety data regularly throughout the trial and make decisions regarding the advisability of continuing accrual to a particular dose cohort, and/or escalating the dose and allowing accrual to a higher dose cohort. In order to do so, the Investigator must ensure to report safety data to the Sponsor or designee in a timely manner. This includes, but is not limited to:

- SAEs must be reported within 24 hours of awareness (SAE report form)
- DLTs must be reported within 24 hours of occurrence
- IRRs of \geq Grade 2 must be reported within 24 hours of occurrence
- All AEs will be reported in the CRF in a timely manner
- Dose-modifications (i.e., dose-reduction, temporary interruptions regardless of cause) will be reported in the CRF in a timely manner
- Local laboratory data will be reported in the CRF in a timely manner

Availability of these data will enable the Sponsor to act promptly in response to safety signals and to ensure Health Authorities, as well as Investigators, who may be participating in other Sym015 clinical trials, are informed of events occurring during this trial.

Safety teleconferences will be held between the Investigational Site(s) and the Sponsor and/or designee. Patients will be carefully evaluated for evidence of all AEs, including potential cumulative and/or delayed toxicities throughout the duration of their time in the trial.

- Part 1: It is intended that safety teleconferences will be held biweekly; however, frequency may fluctuate based on accrual and trial activity, as indicated
- Part 2: It is intended that safety teleconferences will be conducted after enrollment of approximately 15 and 30 patients. If safety concerns emerge, more frequent meetings will be held on an ad hoc basis.

12.2 Other Safety Surveillance Activities

A Medical Monitor is assigned to review and evaluate relevant clinical/safety information concerning the clinical trial. The responsibilities of the Medical Monitor include, but are not limited to:

- Evaluation of coding and trending of AEs in conjunction with the Drug Safety physician
- Performing surveillance on potential safety signals in conjunction with the Drug Safety physician
- Evaluating abnormal laboratory values
- Providing medical support to the Sponsor in answering questions related to the trial protocol
- Updating the SMC on trial status at scheduled meetings

A Drug Safety physician is assigned to review, assess, and approve all SAE cases and associated reports. This physician will also perform the following:

- Assess for safety signals and trends in conjunction with the Medical Monitor
- Assist with questions regarding medical coding of SAEs
- Discussing with the Sponsor Chief Medical Officer, any cases which may present a concern with regard to a signal or safety issue.

